This will be a pilot series of several case reports involving a small number (5) of patients. We will manage and follow patients (daily) for the remaining duration of their hospital stay and (weekly) if they continue study participation in the outpatient setting. We will collect data for the duration of the patient's study involvement to assess the device's medical efficacy. Data collected will be analyzed to determine the ability of the device to isolate fistula effluent, number of required dressing changes, average time of dressing changes, and patient quality of life. A cost analysis will also be performed.

Attachments

[Back to Top](#)

Study Population: Describe the characteristics of the subject population, such as anticipated number, age range, gender, ethnic background and health status. Identify the criteria for inclusion and exclusion. Explain the rationale for the use of special classes such as fetuses, pregnant women, children, institutionalized, adults with impaired consent capacity, prisoners, economically or educationally disadvantaged persons or others who are likely to be vulnerable.

If women or minorities are included, please address how the inclusion of women and members of minority groups and their subpopulations will help you meet your scientific objectives. Exclusion of women or minorities requires clear and compelling rationale that shows inclusion is inappropriate with respect to the health of the subjects or that inclusion is inappropriate for the purpose of the study. Cost is not an acceptable reason for exclusion except when the study would duplicate data from other sources. Women of childbearing potential should not be excluded routinely from participation in clinical research.

Provide the following information:

- A description of the subject selection criteria and rationale for selection in terms of the scientific objectives and proposed study design;
- A compelling rationale for proposed exclusion of any sex/gender or racial/ethnic group;
- The proposed dates of enrollment (beginning and end);
- The proposed sample composition of subjects.

You may reference grant application/sponsor's relevant protocol pages and attach as an appendix using the below attachment button, however, a summary paragraph must be provided in the text box below.

Candidates for this study are patients aged 18 and older admitted to the ICU or trauma and acute care ward at UK hospital.

a. Inclusion Criteria

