Study participants will remain in the ICU/acute care/surgical ward that they were previously admitted to under their attending physician's care, for the remaining duration of their hospital stay. Study involvement will have no effect on determining hospital length of stay, discharge rates, re-admittance, or hospital placement. Data will be collected daily by research personnel or participating healthcare staff while patients remain in the hospital. Patients will periodically be evaluated by research personnel for study purposes. When patients are medically ready for hospital discharge, they (or their LAR, if not yet appropriate for consent) will be involved in a discussion with the PI and their attending physician (if not the PI) on options regarding their transition of care. If patients wish to continue study participation as outpatients, the research team will educate the patient and/or patient's family on device management. If the team decides the patient can effectively manage their device at home, they will be given the option to continue study participation as outpatients. Most EAF patients that are discharged home still require home health visits to manage their wounds. Home health staff will be allowed to dress the surrounding wound bed as normal once the patient has applied their fistula device. Home health staff will be consulted prior to patient discharge on the nature of the study and any concerns addressed. Outpatient study participants will be monitored (weekly) by research staff until fistula resolution or study termination. This will be achieved via phone calls and if able, patients may send photos of their wound to the study team for visualization. Patients will come back to the clinic as necessary per their surgeon's direction. Patients will be given instructions on proper device application and cleaning practices as outpatients. Importantly, patients will be instructed to use water and regular dish soap rather than industrial cleaners, to avoid dishwasher appliances, and to avoid forceful scrubbing or drying of the device.

Attachments

Attach Type	File Name
ResearchProcedures	Outpatient Device Cleaning Form.pdf
ResearchProcedures	Attachment B.pdf
ResearchProcedures	Attachment A rev 1.pdf
ResearchProcedures	UBACC.pdf

Data Collection: List the data or attach a list of the data to be collected about or from each subject (e.g. interview script, survey tool, data collection form for existing data).

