If the research includes survey or interview procedures, the questionnaire, interview questions or assessment scales should be included in the application (use attachment button below).

The data collection instrument(s) can be submitted with your application in draft form with the understanding that the final copy will be submitted to the IRB for approval prior to use (submit final version to the IRB for review as a modification request if initial IRB approval was issued while the data collection instrument was in draft form).

Note: The IRB approval process does not include a statistical review. Investigators are strongly encouraged to develop data management and analysis plans in consult with a statistician.

Data collection will be conducted by study personnel or participating healthcare staff and stored in a secure online application (Sharepoint) within the University of Kentucky.

Primary data points to be collected:

- a. Patient satisfaction/quality of life, as determined by pain rating, mobility scale, and subjective satisfaction questionnaires
 - i. Pain rating 1-10
 - ii. Mobility scale-standard assessment at UK (similar to BMAT)
 - iii. Patient satisfaction can be a version of TAM (technology acceptance model) model, tweaked for patients instead of providers. Give at study completion. Focus on intention to use in future and ease of use.
- b. Number of required dressing changes per day (fistula-specific dressing changes)
- c. Average time of required fistula-specific dressing changes
- d. Terminal wound management that the patient is transitioned to upon study completion
- e. Listing of supplies used each fistula-specific dressing change
- f. Assessment of new technology acceptance by staff-TAM model. Give TAM to nursing staff at study's completion.
- g. If possible and if patient consent is obtained, we will video record the first few device applications/dressing changes per patient case. We will use this video evidence to better design application protocols and strategies in the future.

h. Adverse event assessment form-see Attachment B.

Secondary data points to be analyzed (following study completion):

i. Cost of patient management with device (estimate per week)

j. Effectiveness of device isolation, as determined by infection/complication occurrence, observed leakage, hospital LOS, and resolution times.

Attachments

Attach Type	File Name
DataCollection	Inpatient Data Collection Form rev1 clean.pdf

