Costs to Subjects: Describe any costs for care associated with research (including a breakdown of standard of care procedures versus research procedures), costs of test drugs or devices, and research procedure costs that are the subject's responsibility as a consequence of participating in the research. Describe any offer for reimbursement of costs by the sponsor for research related injury care.

None

Data and Safety Monitoring: The IRB requires review and approval of data and safety monitoring plans for greater than minimal risk research, clinical research, or NIH-funded/FDA-regulated clinical investigations.

If you are conducting greater than minimal risk research, clinical research, or your clinical investigation is NIH-funded/FDA-regulated, describe your Data and Safety Monitoring Plan (DSMP). [Click here for additional guidance on developing a Data and Safety Monitoring Plan.](#)

If this is a *non-sponsored investigator-initiated* protocol considered greater than minimal risk research, clinical research, or your clinical investigation is FDA-regulated, and if you are planning on using a Data and Safety Monitoring Board (DSMB) as part of your DSMP, [click here for additional guidance](#) for information to include with your IRB application.

If relying on an independent agent or committee for DSMB services, it is the PI's responsibility to establish the services with the agent or committee. Please be reminded that the PI must submit DSMB reports to the IRB via modification or continuing review. 

A Data and Safety Monitoring Board will be created to objectively evaluate the study results throughout the course of the study. This board will examine patient adverse events and patient outcomes. The Data and Safety Monitoring Board will consist of a physician (surgeon) and a nurse not affiliated with the study in any way. The DSMB will meet twice for each patient; at 2 weeks post-device initiation or prior to discharge (whichever is first), and at 2 months post-device initiation. The DSMB will review real time data collected by the investigators regarding device usage as detailed in the Data Collection sub-section.

Our Data and Safety Monitoring Plan will include criteria for stopping study enrollment and terminating device usage. These include:

- i. Development of an acute allergic reaction following device usage
- ii. Development of a new EAF, from device use or originating spontaneously

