- iii. Inability to manage device usage at home, as determined by the investigative team
- iv. Unsatisfactory effluent control, as determined by the investigative team

1. Persistent inability of the device to control fistula contents, even after remodeling, refitting, and other modifications have been attempted.

Adverse Events and Serious Adverse Events will be reported per IRB guidelines. Our AE assessment guide is attached (attachment

B). Complications associated with clinical care and underlying disease, and not related the EAF (section 1.1), will not be reported. Patient safety will be monitored normally by hospital staff.

[Back to Top](#)

Subject Complaints: Describe procedures (other than information provided in consent document) for handling subject complaints or requests for information about the research. The procedures should offer a safe, confidential, and reliable channel for current, prospective, or past research subjects (or their designated representative) permitting them to discuss problems, concerns and questions, or obtain information.

If any patient has a complaint at any time during study participation, they may contact their healthcare team or the research personnel and their issues will be discussed. All patients have the right to discontinue study participation at any time.

Does your research involve **Non-English Speaking Subjects or Subjects from a Foreign Culture?**

Yes No

—Non-English Speaking Subjects or Subjects from a Foreign Culture—

Describe how information about the study will be communicated to potential subjects appropriate for their culture, and if necessary, how new information about the research may be relayed to subjects during the study.

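### Follow-up after discharge is limited to patients who choose to continue and are judged able to manage the device at home, so late complications, resolution times and the 2-month DSMB review rest on a selected subset

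*Protocol*

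**What the plan says.** The protocol (Study Design) plans a series of 5 patients, followed "daily) for the remaining duration of their hospital stay and (weekly) if they continue study participation in the outpatient setting". The same section adds: "We will collect data for the duration of the patient's study involvement".

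Research Procedures sets two conditions at discharge. The patient must wish to go on, and the team must be satisfied that home use is feasible: "If the team decides the patient can effectively manage their device at home, they will be given the option to continue study participation as outpatients". Weekly monitoring, by telephone and where possible photographs, then runs until the fistula resolves or the study ends, but only for those who are outpatient participants. Clinic visits are left to the surgeon's direction.

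Four other places bear on this:

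- Data Collection, item j, lists as a secondary data point: "Effectiveness of device isolation, as determined by infection/complication occurrence, observed leakage, hospital LOS, and resolution times".
- Data Collection, item d, records: "Terminal wound management that the patient is transitioned to upon study completion".
- Data and Safety Monitoring gives criteria for stopping enrollment and device use. Criterion iii is "Inability to manage device usage at home, as determined by the investigative team" and criterion iv is "Unsatisfactory effluent control, as determined by the investigative team".
- Data and Safety Monitoring also states: "The DSMB will meet twice for each patient; at 2 weeks post-device initiation or prior to discharge (whichever is first), and at 2 months" after device start. The board is to examine adverse events and patient outcomes, using data that the investigators collect.

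Background puts surgical resolution at 6 to 12 months on average after the fistula develops.

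**The concern.** Device use and outcome follow-up are tied together: a patient who leaves hospital without continuing on the device also leaves data collection. Complications and resolution after discharge are then seen only in patients who passed both conditions.

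The selection is unlikely to be neutral. The discharge condition asks much the same question as criterion iii, which the protocol itself treats as a reason to end device use. A patient whose device was stopped under criterion iii or iv likewise has no outpatient follow-up. Dexterity, family help and personal preference also enter, and a continuer can still fail later, so the subset is not made up purely of device successes. The likely direction nevertheless favours the device.

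Two things are at stake. Complications serve both as a safety outcome and as part of item j, and resolution time is also part of item j; both would be missing for reasons connected with device performance. The DSMB's second look at a patient could also take place with no data after discharge.

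**Working it through.** **Who has data, and when**

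| Patient | In hospital | After discharge |
|---|---|---|
| Wishes to continue and judged able | daily | weekly, to resolution or study end |
| Declines, or judged unable | daily | management moved to (item d), then nothing planned in the text shown |
| Stops the device but stays in hospital | daily | same conditions at discharge |

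The gap is therefore confined to non-continuers, from discharge onward. The DSMB schedule makes no exception for them.

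**Inputs.** From the protocol: 5 patients; second DSMB review at 2 months after device start; first review at 2 weeks or before discharge, whichever comes first. The protocol states no retention rate, no discharge times and no derivation of the sample size, so there is no planned figure to reproduce. The number of non-continuers *k* and the discharge week below are assumptions.

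**Bounds on the complication proportion.** Suppose *k* of 5 do not continue, are discharged before resolution, and no continuer has a post-discharge complication. The true proportion among all 5 then lies between 0 and *k*/5.

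| *k* | Range for post-discharge complications | Resolution time known in at most |
|---|---|---|
| 1 | 0/5 to 1/5 (0–20%) | 4 of 5 |
| 2 | 0/5 to 2/5 (0–40%) | 3 of 5 |
| 3 | 0/5 to 3/5 (0–60%) | 2 of 5 |

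If continuers do have complications, both ends of the range move up, but the width stays *k*/5.

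**Chance of complete follow-up.** If each patient continues independently with probability *q*, all 5 have post-discharge data with probability *q*^5: 59% at *q* = 0.9, 33% at 0.8, 17% at 0.7, 8% at 0.6 and 3% at 0.5.

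**Gap before the second DSMB review.** Two months is 2 × 365.25 / 12 / 7 = 8.7 weeks. For a non-continuer discharged *w* weeks after device start, the period without secured research data is 8.7 − *w*.

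| Discharge week *w* | Weeks without data | Share of 8.7 weeks |
|---|---|---|
| 2 | 6.7 | 77% |
| 4 | 4.7 | 54% |
| 6 | 2.7 | 31% |

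Discharge within 2 weeks is a case the protocol foresees, since the first DSMB meeting is brought forward to precede discharge if that comes sooner.

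**The case against.** The strongest reply has five parts.

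- **The outcomes concern isolation by the device.** Leakage exists only while the device is worn, and length of stay is complete at discharge. Once a patient moves to other management, infection and resolution also reflect that management, and resolution depends heavily on surgical timing. This limits what off-device data say about isolation. It does not remove the need for them: item j is not restricted to time on the device, and delayed harm is a safety question in any case.
- **The bias is inferred.** The discharge condition names home management, not effluent control, and poor control in hospital is seen in the daily data. That is fair, and the direction is likely rather than demonstrated. But inability to manage at home is a termination criterion in its own right, and a device stopped for either reason leaves the patient without follow-up after discharge.
- **Patients may withdraw at any time.** They may, and no rule can guarantee all 5. Declining to use the device at home is, however, different from refusing a telephone call or chart review, and the protocol does not separate the two.
- **The DSMB reviews device-usage data and will hold the inpatient record; long stays are common.** Every patient is indeed to be reviewed once by discharge, and those still in hospital at 2 months have daily data. The board's stated remit nevertheless includes adverse events and outcomes, and nothing secures these for a non-continuer discharged before 2 months.
- **The consent form, adverse event guide and data forms are not shown, and clinic records may hold some data.** This stands as a limit. If those documents already provide the follow-up, the correction is to the protocol text. Clinic visits as directed by the surgeon are not planned study data collection.

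The numerical illustrations rest on assumed non-continuation and discharge times. In a case series each patient can be described individually, but a description cannot supply outcomes that were not collected.

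**Conclusion.** The concern holds. Followed as written, the protocol obtains late complications and resolution times only from patients who wish to continue and are judged able to manage the device at home. That selection is plausibly related to how the device performs. The rule also does not secure the data needed for the 2-month DSMB review of every patient. This concerns how the study is conducted, so an analysis plan could not repair it.

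Each non-continuer discharged before resolution leaves one fifth of the post-discharge complication proportion undetermined. For discharge 2 to 6 weeks after device start, 77% down to 31% of the period up to the second DSMB review is uncovered. How many patients this would affect cannot be known from the protocol; it could be none if all continue or stay in hospital. Confidence is medium because of the attachments not shown. The point should be corrected, given how little the correction costs.

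**What to change.** Amend Study Design and Research Procedures as follows:

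- Every patient who received a device stays in outcome follow-up until fistula resolution or study end, whether or not the device is still in use, unless consent to follow-up is withdrawn. A call or chart review covering complications, current wound management and fistula resolution is enough.
- The reason for not continuing is recorded for each patient.
- Stopping for inability to manage at home or for poor effluent control (criteria iii and iv) is counted as an outcome.
- Results are reported with all treated patients in the denominator.
- The follow-up rule is reconciled with the 2-month DSMB review, so that the board has adverse event and outcome data on each patient.

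If the consent form or data forms already provide this follow-up, bring the two sections into line with them.

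The cost is a few extra calls or chart checks for at most 5 patients, and one consent-form sentence separating stopping the device from stopping follow-up. No new procedure or staff is needed, and nothing changes about who uses the device at home.

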We anticipate the use of this device will vastly reduce the cost, both labor costs and dressing supply costs, of managing EAF patients as compared to NPWT management. We believe it will greatly improve patient mobility, comfort, quality of life, and offer an easier way to manage enteroatmospheric fistulas than many current options. Ultimately, using this device for EAF care could provide a cost effective but efficacious option for patients that cannot afford or do not wish to participate in NPWT management. This study will collect financial data in addition to clinical data points and at its conclusion we will conduct an in-depth cost analysis.

Due to patenting prior art, similar fistula isolation devices being trialed [4], and commercialization issues, we are not seeking a novel medical device patent. The device design, the novelty of its 3D printing manufacturing process, and its significant customizability differentiate it substantially enough from prior art to not infringe on patenting or copyright laws but do justify this clinical investigation. This study has no commercial interests and we are not seeking to market our device at this time.

This device would be classified as a Class II wound care device. Because of that classification, it does not necessitate an Investigational Device Exemption (IDE) from the FDA, unless it is determined to pose Significant Risk (SR) to the patient. Thus, our study is contingent on the University of Kentucky IRB determining the use of our device as Non-Significant Risk (NSR). Due to prior, similar devices being deemed NSR, we believe our device should likewise be approved. The novelty of our device involves its production and customizability, not its composition. All materials used are FDA approved for biocompatibility, and our 3D printers are also FDA approved for clinical use (see attachment A for more details and safety information). The open abdomen setting in which this device would be used is a non-sterile, externally located field and our device meets all FDA Good Manufacturing Practices in such settings. If the IRB approves our device as NSR, this study will be conducted as an IDE-expedited study, falling solely under University of Kentucky IRB regulation.

References

1. Bobkiewicz et al. Management of enteroatmospheric fistula with negative pressure wound therapy in open abdomen treatment: a multicenter observational study. *International Wound Journal* 2016; 14.

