Objectives: List your research objectives. You may reference grant application/sponsor's relevant protocol pages and attach as an appendix in the E-IRB "Additional Information" section, however, a summary paragraph must be provided in the text box below.

Our primary objective is to create a viable EAF management solution independent of NPWT.

Our secondary objectives include observing a decrease in required dressing changes, a decrease in healthcare costs to patients, and an increase in patient satisfaction.

Study Design: Describe the study design (e.g., single/double blind, parallel, crossover, etc.). Indicate whether or not the subjects will receive placebo medication at some point in the research procedures. Also, indicate whether or not the subjects will be randomized in

this study. You may reference sponsor's protocol pages and attach as an appendix in the E-IRB "Additional Information" section, however, a summary paragraph must be provided in the text box below. (Including the study design table from a sponsor's protocol is helpful to IRB members.)

Community-Based Participatory Research: If you are conducting [community-based participatory research \(CBPR\)](#), describe strategies for involvement of community members in the design and implementation of the study, and dissemination of results from the study.

Research Repositories: If the purpose of this submission is to establish a Research Repository (bank, registry) indicate whether the material you plan to collect would or would not be available from a commercial supplier, clinical lab, or established IRB approved research repository. Provide scientific justification for establishment of an additional repository collecting duplicate material. Describe the repository design and operating procedures. For relevant information to include, see the UK Research Biospecimen Bank Guidance [\[PDF\]](#) or the UK Research Registry Guidance [\[PDF\]](#)

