Patients will be followed by physicians, nurses, and other staff throughout the patient's hospital stay and study duration. Skin and wound protection and patient comfort will be a priority when applying dressings and the 3D printed device. Any emergent developments will be handled per standard of care by the respective healthcare team. Patient information will remain confidential at all times within the patient's medical record, the paper study source records (which will be kept under lock and key in the PI's office [C207] or the General Surgery Research office [C243] when not in use), and within the secure SharePoint site once entered into electronic database. Only the patient's healthcare team and approved research personnel will have access to patient information. Patient information will be used only for clinical management and research purposes.

Benefit vs. Risk: Describe potential benefits to the subject(s); include potential benefits to society and/or general knowledge to be gained. Describe why the risks to subjects are reasonable in relation to the anticipated benefit(s) to subjects and in relation to the importance of the knowledge that may reasonably be expected to result. If you are using vulnerable subjects (e.g., impaired consent capacity, pregnant women, etc...), justify their inclusion by describing the potential benefits of the research in comparison to the subjects' vulnerability and the risks to them. For information about inclusion of certain vulnerable populations, see the IRB/ORI Standard Operating Procedure for Protection of Vulnerable Subjects [C3.0100] [\[PDF\]](#).

- a. Risk: skin irritation, device dislodgement, potential fistula leakage, abdominal binder discomfort.
- b. Benefit: increased patient mobility, decreased patient and system cost, decreased dressing changes, decreased dressing change time, increased patient quality of life, potential decreased fistula leakage.

Available Alternative Treatment(s): Describe alternative treatments and procedures that might be advantageous to the subjects, should they choose not to participate in the study. This should include a discussion of the current standard of care treatment(s).

Patients that refuse study participation will receive appropriate EAF/OA management in accordance with their attending physician's directions.

[Back to Top](#)

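### Item a of Data Collection can describe pain, mobility and device acceptance, but not overall quality of life or an increase in quality of life or satisfaction

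*Protocol*

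**What the plan says.** All of the relevant text is in the Protocol's Research Description.

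- **Study Design** describes the trial thus: "This will be a pilot series of several case reports involving a small number (5) of patients". Among the things to be determined from the data it lists "number of required dressing changes, average time of dressing changes, and patient quality of life".
- **Benefit vs. Risk** includes "increased patient quality of life, potential decreased fistula leakage" among the benefits.
- **Background** is more emphatic: "We believe it will greatly improve patient mobility, comfort, quality of life".
- **Objectives** does not name quality of life. The nearest secondary objective is "an increase in patient satisfaction".
- **Data Collection, item a**, gives the only definition: "Patient satisfaction/quality of life, as determined by pain rating, mobility scale, and subjective satisfaction questionnaires". Its sub-items are a pain rating from 1 to 10, the hospital's standard mobility assessment, and a satisfaction measure. The last is worded tentatively: it can be a version of the technology acceptance model (TAM) adapted for patients, given at study completion and centred on future intention to use and ease of use.
- **Data Collection, item f**, gives a TAM form to nursing staff and describes its purpose as assessing acceptance of new technology.
- **Research Procedures** has inpatient data collected daily and outpatients monitored weekly. It gives no separate schedule for pain, mobility or satisfaction.

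**The concern.** An outcome's label should match what is asked of the patient. Here the label includes quality of life, while the stated content is one symptom, one function and a form that, as described, concerns the device. A patient may find the device easy to use and intend to keep using it while their life is no better, or the reverse. If the text is followed as it stands, a good acceptance score could be reported under the name of quality of life.

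There is also a problem of timing. Objectives seeks a rise in satisfaction and Benefit vs. Risk a rise in quality of life. A rise needs an earlier value for comparison, and the only satisfaction form described is given once, at the end.

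An analysis plan written later cannot repair this. It can decide how to summarise answers, but it cannot supply a question that was not asked or a pre-device value that was not collected.

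**Working it through.** The Protocol gives no figure for this outcome, so there is none to reproduce. The check compares the definition with the uses made of it.

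**Step 1. What each component can show.**

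| Component (Data Collection, item a) | What it covers | Timing in the text | What it can support |
|---|---|---|---|
| Pain, 1 to 10 | One symptom | None of its own; inpatient data are daily in general | A description of pain, over time if it is on the daily form |
| Local mobility scale | One function | As for pain | A description of mobility, on the same condition |
| Satisfaction questionnaires; the one described may be an adapted TAM form | Intention to use and ease of use | Once, at completion | Device acceptance at the end |

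None of the three is described as asking about overall quality of life.

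**Step 2. Whether the Protocol itself treats these as quality of life.** Benefit vs. Risk lists greater mobility and better quality of life as two separate benefits, and Background likewise names mobility, comfort and quality of life side by side. Item a then uses mobility to define quality of life. Item f treats TAM in staff as a measure of technology acceptance, whereas item a places a version of it under satisfaction and quality of life.

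**Step 3. Whether an increase can be shown.** Within-patient change = later value − earlier value. With one satisfaction form per patient:

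- values available: 5 patients × 1 = 5
- within-patient differences: 5 × (1 − 1) = 0

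There is no control group to supply a comparison either. For pain and mobility a pre-device value may exist, because Subject Recruitment Methods & Privacy starts data collection once consent is given and Research Procedures has the device made and then applied at the next dressing change. The text does not say that such a value will be taken.

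**Step 4. What 5 patients could show with a suitable item.** Take the most favourable case, in which all 5 improve:

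- exact sign test, one-sided: 0.5^5 = 0.03125
- two-sided: 2 × 0.03125 = 0.0625
- lower limit of the exact 95% interval for the proportion improving: 0.025^(1/5) = 0.478

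Even then the lower limit is below one half, and without a control group an improvement could not be attributed to the device. A better item would correct what is being described, but the result would remain descriptive.

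**The case against.** The strongest case on the other side has five parts.

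1. **Pain and mobility bear on quality of life.** This stands. A reader might infer that the trial can say nothing relevant to quality of life. The documents do not support that: both are recognised domains, Background links mobility with quality of life when discussing negative pressure therapy, and daily inpatient collection may allow both to be followed over time. The limit is on statements about overall quality of life.
2. **No composite is stated.** This also stands. A reader might infer that the three parts are to be merged into one score and that a combining rule is missing. Item a lists them separately and nowhere says they will be summed. Scoring is commonly left to an analysis plan, so its absence here is not a defect.
3. **The forms are not shown.** The inpatient and outpatient forms are listed as attachments, item a speaks of questionnaires in the plural, and the TAM wording is tentative. So it cannot be said that no patient is ever asked about quality of life. But item a states what the outcome is determined by, and if the forms ask more, the text should say so.
4. **Background and Benefit vs. Risk state expectations.** This is fair, and quality of life is not a listed objective. Study Design, however, names it as something the data will be analysed to determine, and that is not merely a hope.
5. **This is a case series of 5, so little turns on it.** The size limits any conclusion, but it does not excuse a label that the content does not bear out. In a small descriptive series the outcome's name is much of what readers take away.

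**Conclusion.** The concern holds in a limited form. As written, item a can support separate descriptions of pain, mobility and device acceptance. It cannot support a statement about overall quality of life, which Study Design says will be analysed, or about the increase listed under Benefit vs. Risk. A satisfaction form given only at completion cannot show the increase named in Objectives.

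On size: none of the three components is described as asking about overall quality of life, and the satisfaction form gives no within-patient change in any of the 5 patients.

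This rests on two assumptions: that the attached forms contain no quality-of-life item and no earlier satisfaction question beyond what item a describes, and that the TAM version is the satisfaction form used. If the forms hold more, the defect shrinks to a definition that needs to be brought into line with them. The point does not affect safety monitoring or the dressing-change outcomes, but it should be settled before data are collected.

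**What to change.** **Minimum change.** In Study Design and in Data Collection item a, replace the merged outcome with three separately named descriptive outcomes: pain, mobility and patient device acceptance. State that no overall quality-of-life conclusion will be drawn from them. This costs wording only. Under this option, Objectives should speak of satisfaction or acceptance at completion, unless a pre-device satisfaction question is added.

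**If quality of life is to remain an analysed outcome.** Add one global patient-rated quality-of-life item and one satisfaction item. Word the satisfaction item about the patient's current fistula management, so that it can be answered before the device is in use. Ask both before first device application and then at the existing inpatient and weekly outpatient contacts. Base any quality-of-life statement on the global item alone, and report the acceptance form under its own name.

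**Cost.** One or two extra questions per contact, with no additional visits. State in either case that, with 5 uncontrolled patients, these results are descriptive.
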